5. STUDY VARIABLES AND DEFINITIONS

5.1. EFFICACY VARIABLES

5.1.1. Primary Efficacy Variable

The primary efficacy variable is the weekly mean pain intensity score calculated using the 'average pain over the last 24 hours' scores collected in the daily diaries using an 11-point scale where 0 = no pain, and 10= pain as bad as you can imagine. The weekly mean pain intensity score will be defined as the sum of non-missing daily "average pain over the last 24 hours" scores reported during that week (Days -7 to -1 [Baseline], Days 1-7 [Week 1], Days 8-14 [Week 2], Days 15-21 [Week 3], . . . , Days 50-56 [Week 8]) divided by the number of days with non-missing scores for that week. If a subject reports less than 3 days of pain scores during a week, the weekly mean pain intensity score will be set to missing.

The primary efficacy endpoint is defined as the change from baseline at Week 8 with respect to the weekly mean of the daily 24-hour pain intensity for the index joint. This will be compared between the CR845 and placebo group.

5.1.2. Secondary Efficacy Variables

The following will be secondary efficacy variables/endpoints and will be compared between the CR845 and placebo group:

- Change from baseline in the Western Ontario & McMaster Osteoarthritis (WOMAC) Index Total Score at each week
- Change from baseline in the WOMAC Pain Intensity, Stiffness and Function Sub-scale Scores at each week
- Treatment Pain Response: Proportion of patients with at least 30% and 50% improvement from baseline in the weekly mean pain intensity at week 8
- Patient Global Impression of Change (PGIC) at Week 8 or End of Treatment visit
- Supplemental Analgesic Medication Used: Average daily number of acetaminophen tablets used over the study and during the Maintenance Treatment Period
- Proportion of patients withdrawing from treatment due to lack of analgesic efficacy

Western Ontario & McMaster Osteoarthritis (WOMAC) Index

The WOMAC Index is a self-administered assessment used to measure pain, stiffness, and physical function in patients with osteoarthritis. The WOMAC Index contains 24 questions across 3 different sub-scales (pain, stiffness, and function) all with scoring 0-10 (0 = No Pain/Stiffness/Difficulty, 10 = Extreme Pain/Stiffness/Difficulty). The WOMAC Index Total Score is calculated as the sum of all 24 scores. Each WOMAC Index Subscale score (Pain/Stiffness/Function) is calculated as the sum of all scores within that subscale. Patients will complete the WOMAC at each clinic visit starting with the Baseline Visit.

Treatment Pain Response

A patient's pain response to treatment is defined as the percent improvement from baseline with respect to the weekly mean of "average pain in the last 24 hours" pain score during the last week of the Maintenance Treatment Period (Week 8) . If a patient's mean weekly pain score during the last week of the Maintenance Treatment Period is greater than the baseline score (i.e., the patient has an increase in pain compared to baseline), his/her response to treatment will be assigned a value of 0 (i.e. the patient will be considered a non-responder). Patients who discontinue study drug early will be considered non-responders to treatment and will be assigned a pain response of 0.

The percentage of subjects achieving levels of treatment response 10% to 100% by 10% increments as defined above will be calculated with 30% of key interest as it has been shown to represent a clinically important improvement in pain.

Patient Global Impression of Change (PGIC)

The PGIC score collected at Week 8, or at the End of Treatment visit (for patients who discontinue treatment early) ranges from 1 (Very Much Improved) to 7 (Very Much Worse).

Supplemental Analgesic Medication Used

The average daily number of acetaminophen tablets used during the study will be calculated using data recorded in the patient diary as the sum of the total number of tablets used divided by the length of exposure (in days). A similar algorithm will be used to derive the average daily number of acetaminophen tablets used during each week (baseline will be study day -5 to study day -1), the Titration-to-Effect Period, the Maintenance Treatment Period, Study Day 1 to 56 Period and the End of Treatment week

Due to the nature of the data, the average daily number of analgesic rescue use (in this case acetaminophen) tend to have a large portion of zeroes (contributed by subjects not taking any supplemental pain medication) followed by continuous distribution of non-zero values. Therefore, the supplemental pain medication for OA will be grouped categorically into the following classes: (1) no supplemental acetaminophen tablets, (2) 0 to \leq 0.5 tablets, (3) $>$ 0.5 to \leq 1.0 tablets, (4) $>$ 1.0 to \leq 2.0 tablets, and (5) $>$ 2.0 tablets.

Withdrawal Due to Lack of Analgesic Efficacy

This will be obtained from the treatment completion form of the eCRF.

5.2. SAFETY VARIABLES

The safety variables are:

- Adverse events
- Clinical laboratory evaluations (including serum sodium levels)
- Vital signs : systolic blood pressure, diastolic blood pressure, heart rate, respiratory rate and body temperature
- ECGs: heart rate, PR interval, QRS duration, QT interval, RR duration, QTcF, and clinical interpretation of ECG test results

5.2.1. Adverse Events

Adverse events that occur after the signing of the informed consent up to study completion, including the Follow-up visit 7-10 days after the last dose of study medication, will be recorded on CRFs for all subjects who enter the study. An additional follow-up telephone call may be performed up to 30 days after the last dose as a final assessment of treatment-emergent adverse events unresolved at the final clinic visit attended. Information gathered by telephone related to status of adverse events will be documented in the patient case report form.

5.2.2. Clinical Laboratory Evaluations

The following clinical laboratory tests will be performed at Screening, Day 1 (Baseline prior to drug administration) and at Day 57 (or early termination), with additional blood sampling for the valuation of serum sodium as follows:

Table 2 – Clinical Laboratory Tests

Hematology:	Hemoglobin, hematocrit, red blood cell (RBC) count, RBC indices, mean corpuscular hemoglobin (MCH), mean corpuscular hemoglobin concentration (MCHC), platelet count (or estimate), white blood cell (WBC) count including differential.
Serum Chemistry:	Total bilirubin, ALT, AST, glucose (fasting/non-fasting), serum creatinine, Blood Urea Nitrogen (BUN), electrolytes (sodium, potassium, chloride, and calcium), alkaline phosphatase, gamma glutamyl transferase, and creatinine.
Serum Sodium	Serum sodium levels will be measured at each clinic visit. If at any time during the study, the patient's serum sodium level is > 150 mmol/L, dosing should be paused and the patient should be evaluated. Based upon the outcome of the clinical evaluation of the patient by the clinical staff, the dosing of study medication will either be: a) restarted or b) terminated.

The following laboratory tests will also be performed:

- For female patients of childbearing potential, a serum pregnancy test will be conducted at Screening and a urine pregnancy test will be conducted at the Day 1 (Baseline) visit prior to the administration of study drug.
- Urine drug screen at Screening for amphetamines, barbiturates, benzodiazepines, cocaine, opioids, phencyclidine (PCP), and tetrahydrocannabinol (THC).

Blood samples for hematology and serum chemistry will be sent to a central laboratory for analysis. Urine drug screens, pregnancy tests, and sodium levels will be conducted at the study sites.

5.2.3. Vital Signs

Vital sign measurements of systolic blood pressure, diastolic blood pressure, heart rate and respiratory rate will be obtained at each clinic visit. Body temperature (T) will only be obtained at Screening and Day 57 (or early termination).

[figure not shown]
At screening, blood pressure and heart rate will be assessed both in the supine and standing position. For the purpose of these evaluations, patients should be assessed in the supine position first and then, after sitting up for at least one-minute, should be standing for at least 3 minutes prior to measuring blood pressure or heart rate. Otherwise, all vital signs will be collected while the patient is at rest in a seated position.

5.2.4. ECGs

An ECG will be performed at Screening and Day 57 (or early termination) and will consist of heart rate, PR duration, QRS duration, QT interval, RR interval, uncorrected QT interval and corrected Fridericia's QT interval. The investigator will interpret the ECG as Normal, Abnormal – Not Clinically Significant or Abnormal – Clinically Significant.

6. SAMPLE SIZE DETERMINATION

Approximately 405 patients with OA of the hip and knee will be randomized in a 2:1 ratio (270 to CR845 and 135 to placebo) at approximately 40 sites in the United States.

A sample size re-estimation will be made after approximately 50% of the planned 405 patients have been randomized and have either completed the 8-week treatment period or have discontinued from treatment early (see Section 8.3).

The sample size will be calculated to ensure 90% conditional power such that:

$$t_2 \geq \frac{1.96 + \sqrt{0.5} t_1}{\sqrt{0.5}}$$

where t_1 and t_2 are the t-statistics from separately performing the primary analysis for stage 1 (interim) and stage 2 (post interim) patients respectively (see Section 8). Maintaining a 2:1 ratio, the required total sample size (n_2) to achieve the above criteria will be calculated using the difference between least square means and the corresponding standard error divided by $\sqrt{1/n_{11} + 1/n_{12}}$ from stage 1 analysis (where n_{11} and n_{12} are the sample size in each treatment group from stage 1).

A maximum total sample size of 480 randomized patients will be allowed for the study regardless of the sample size re-estimation at the interim analysis.

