10.1. PRIMARY EFFICACY VARIABLE

To account for the interim unblinded sample size re-assessment, the analyses relating to the primary efficacy variable will employ weighted test statistics as proposed by Cui, Hung and Wang in order to maintain the 5% two-sided type 1 error rate. As there is no potential for early stopping of the study, no adjustments need to be made to the significance levels for the combined final analysis. The primary analysis and sensitivity analyses described in this section will be performed on each stage (pre and post interim patients) separately and test statistics (t_1 and t_2) from each stage will be combined to obtain the CHW Z statistic as follows:

$Z_{CHW} = \sqrt{0.5} t_1 + \sqrt{0.5} t_2$ from which the two-sided p-value will be obtained using the normal distribution.

Point estimates and 95% CI will be obtained using methodology suggested by Hung and Lawrence²:

Point estimate:

$$\hat{\delta} = \frac{t_1 \hat{\delta}^{(1)} + \sqrt{1-t_1} \sqrt{t^* - t_1} \hat{\delta}^{(2)}}{t_1 + \sqrt{1-t_1} \sqrt{t^* - t_1}}$$

where

$t_1 = 0.5$

$t^* = (\text{Re-estimated total sample size})/405$

$\hat{\delta}^{(1)}$ = Least square mean difference from stage 1 analysis

$\hat{\delta}^{(2)}$ = Least square mean difference from stage 2 analysis

$$95\% \text{ CI} = \hat{\delta} \pm \left(\frac{\hat{\delta}}{Z_{CHW}} * 1.96 \right)$$

The primary analysis and each sensitivity analysis will also be performed using the full combined dataset with no CHW adjustment. Presentation of results will start with these analyses (additionally including the CHW results) and then follow with the results of the analysis from each individual stage.

The primary efficacy variable will be analyzed using a mixed effect model with repeated measures (MMRM). The model will contain treatment (placebo vs CR845), treatment-by-week interaction as fixed effects, baseline value and OA joint (hip vs knee) as covariates, and patient as a random effect.

The treatment difference between CR845 (across all doses) and placebo at Week 8 (the primary efficacy endpoint) will be estimated as the simple contrast in the treatment effect. The 2-sided 95% confidence interval (CI), based on the difference in the least squares (LS) means between the 2 treatment groups (CR845 vs placebo) will be presented. The LS means (and 95% CI) will be additionally be presented for each treatment for each week.

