- Combine datasets from 2 and 3 with all data imputed and keep for Step 5.

Step 4 - Impute missing data due to reasons other than AE or LOTE

If the patient discontinues due to reasons other than AE or Lack of Efficacy, at each time point, missing data will be assumed to follow a distribution similar to scores for patients who are still in the study and randomized to the same treatment group.

- To impute missing data at the first week x with any missing data not due to AE/LOTE, the following will be performed to the MONOTONIC dataset:
 - Split the MONOTONIC data into 2 datasets
 - 1) Non-missing at Week x or missing at Week x and discontinued treatment not due to AE/LOTE
 - 2) Missing at Week x and discontinued treatment due to AE/LOTE – discard data
 - Sort dataset (1) by imputation and subject number
 - Impute the missing data at week x in dataset (1) as follows:

```
proc mi data=DATA1 out=WEEKx seed=543571857 n impute=1;
by Imputation ;
var TRTPN STRATAN BASE NRSWEEK1-NRSWEEKx;
monotone regression;
run;
```
 - Set any imputed values <0 or >10 to 0 and 10 respectively.
- To impute missing data at the next week y with any missing data not due to AE/LOTE, the following will be performed to the WEEKx dataset:
 - Split the WEEKx data into 2 datasets

- 3) Non-missing at Week y or missing at Week y and discontinued treatment not due to AE/LOTE
- 4) Missing at Week y and discontinued treatment due to AE/LOTE – discard data
 - Sort dataset (3) by imputation and subject number
 - Impute the missing data at week y in dataset (3) as follows:

```
proc mi data=DATA3 out=WEEKY seed=543571857 n impute=1;
by _Imputation_;
var TRTPN STRATAN BASE NRSWEEK1-NRSWEEKx;
monotone regression;
run;
```
 - Set any imputed values <0 or >10 to 0 and 10 respectively.

- Continue in similar fashion until no missing data with dataset including either completers or those that discontinued treatment not due to AE/LOTE.

Step 5 – Combine datasets back together and re-structure back as per ADaM

Combine final datasets from Steps 3 and 4. Sort by imputation and subject number. Re-structure dataset to be univariate with a Week (AVISITN = 1, 2,3 ,4 ,5 ,6 7, 8) and AVAL (using NRSWEEK1 to NRSWEEK8) and CHG (AVAL-BASE) variable. (MMRMDATA)

Step 6 – Perform MMRM on each imputed dataset

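### The SAP's conditional-power criterion for sample-size re-estimation carries a sign that cannot be derived from its own final test

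*SAP*

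**What the plan says.** SAP Section 6 requires the sample size to give 90% conditional power for the event "t_2 \geq \frac{1.96 + \sqrt{0.5} t_1}{\sqrt{0.5" (the extracted text is LaTeX; in full, t2 ≥ (1.96 + √0.5·t1)/√0.5). It defines both statistics together: they "are the t-statistics from separately performing the primary analysis for stage 1 (interim) and stage 2 (post interim) patients respectively". The stage 2 size is then "calculated using the difference between least square means and the corresponding standard error" from stage 1, keeping 2:1 allocation, with a maximum of 480 patients in total.

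SAP Section 10.1 gives the final test as "Z_{CHW} = \sqrt{0.5} t_1 + \sqrt{0.5} t_2", "from which the two-sided p-value will be obtained using the normal distribution". The two-sided level is 5%, with no adjustment for the interim.

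The sign convention for t1 and t2 is not stated in either section. The indirect evidence is as follows. Pain is recorded "using an 11-point scale where 0 = no pain, and 10= pain as bad as you can imagine" (SAP 5.1.1). Step 5 of the programming plan in SAP 16.1 forms an AVAL "and CHG (AVAL-BASE) variable". Section 10.1 describes the estimate as the "difference in the least squares (LS) means between the 2 treatment groups (CR845 vs placebo").

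**The concern.** The event used for conditional power should be the event that the final test will be significant in favour of CR845, given the interim result. That event comes from solving Z_CHW for t2. The printed inequality has t1 with a plus sign on the right while t2 stands unsigned on the left, so it constrains the difference t2 − t1. The final test uses the sum t1 + t2.

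This is the only formula in the text reviewed that sets the target sample size. The Protocol Synopsis says only that re-estimation is based on conditional power, and Protocol 11.1 gives the SAP precedence. The calculation is done on unblinded data, where the rule should not need repair by whoever programs it. From the same interim data, two competent readers could arrive at no increase or at the 480 cap.

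**Working it through.** **Inputs.** Effect size 0.343, 270:135 patients and more than 90% power (Protocol Synopsis, sample size). Interim at about 50% of 405, cap 480, 90% conditional power (SAP 6). Weights √0.5 and two-sided 5% (SAP 10.1). Assumed here: normal approximation, conditional power evaluated at the stage 1 estimate, n1 = 202.5, and n2 as the stage 2 size over both arms.

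**The plan's own power figure.** 0.343·√(270·135/405) = 0.343·√90 = 3.254, and Φ(3.254 − 1.96) = 0.902. The stated power reproduces.

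**Solving the final test for t2.** 1.96/√0.5 = 2.772.

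- Positive favours CR845: √0.5(t1 + t2) ≥ 1.96 gives t2 ≥ 2.772 − t1.
- Negative favours CR845: √0.5(t1 + t2) ≤ −1.96 gives −t2 ≥ 2.772 + t1.
- Printed: t2 ≥ 2.772 + t1.

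At the printed boundary, Z_CHW = 1.96 + 2·√0.5·t1, which equals 1.96 only when t1 = 0. For t1 = 1, 2 and 2.3 it is 3.37, 4.79 and 5.21. This step needs no assumption about effect or timing.

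**Size at the planned effect.** Expected |t1| = 0.343·√(135·67.5/202.5) = 0.343·√45 = 2.301, and z(0.90) = 1.2816.

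*Rule consistent with Z_CHW.* The hurdle is 2.772 − 2.301 = 0.471. Then n2 = 202.5·((0.471 + 1.2816)/2.301)² = 117.5, a total of 320, so no increase. Conditional power is Φ(2.301 − 0.471) = 96.6% at 405, and 98.7% at 480 (n2 = 277.5).

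*Case A: negative favours CR845, printed line read literally.* With t1 = −2.301 the event is t2 ≥ +0.471, a stage 2 result favouring placebo.

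- At 405: 1 − Φ(0.471 + 2.301) = 0.28%.
- At 480: 1 − Φ(0.471 + 2.301·√(277.5/202.5)) = 0.08%.
- The probability falls as n2 grows. Its upper limit, as n2 tends to 0, is 1 − Φ(0.471) = 32%.
- Reaching 90% requires 2.772 + t1 < −1.2816, so it is impossible for t1 between −4.05 and 0.
- If the minus sign on t2 is restored, or n2 is solved from the squared difference, the consistent answer (n2 about 117) returns.

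*Case B: positive favours CR845, printed line read literally.* The hurdle is 2.772 + 2.301 = 5.073. Then n2 = 202.5·((5.073 + 1.2816)/2.301)² = 1,544, a total of 1,747, so the cap applies. Taking both statistics as magnitudes gives the same result. A total within 480 needs t1 ≥ (2.772 + 1.2816)/(√(277.5/202.5) − 1) = 23.8. The consistent rule needs no increase once t1 ≥ 4.0534/2 = 2.03. Under the planned effect that happens with probability 1 − Φ(2.027 − 2.301) = 61%; at half the effect it is 19%.

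| Interim size (assumed range) | Consistent total | Case A at 405 | Case A upper limit | Case B total | P(no increase needed) |
|---|---|---|---|---|---|
| 190 to 215 | 317 to 323 | 0.18% to 0.43% | 29% to 34% | 1,700 to 1,794 | 60% to 61% |

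The conclusions do not change over this range.

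**The case against.** The strongest reply is that the documents point to case A and give case B no direct support. High pain is bad and change is value minus baseline. The code in SAP 16.1, Step 6, requests LS-mean differences for a class variable whose levels are CR845 and Placebo; with default alphabetical ordering that is CR845 minus placebo, so benefit is negative. The right-hand side of the printed criterion is then the correct hurdle, and only a minus sign or modulus on t2 is missing. A programmer who solves for n2 squares the standardised difference and gets about 117. One who reads the line literally finds no solution and would notice. On this view the slip is notational, and the extra-patient figures belong to a reading that the SAP does not invite.

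Three further points are fair. Under case B the consistent rule itself goes to 480 when t1 is below 4.0534/(1 + √(277.5/202.5)) = 1.87, so the two rules agree there; that is Φ(1.867 − 2.301), about one third of trials under the planned effect and about three quarters at half of it. SAP 8.3 and Protocol 11.3, where an interim rule or sign convention would naturally sit, were not in the text reviewed. A sign or modulus bar lost in PDF extraction cannot be excluded, although the minus signs in the point-estimate formula of SAP 10.1 survived.

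All of this limits the consequence. It does not rescue the formula. Both statistics are defined alike and added with equal positive weights, so no shared orientation makes the printed line agree with Z_CHW. Only a mixed convention would do so, and neither Section 6 nor Section 10.1 states one.

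**Conclusion.** The concern holds: as printed, the re-estimation criterion is inconsistent with the final test under either orientation. The algebra rests on no assumption beyond t1 and t2 sharing one sign convention.

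The practical effect depends on implementation. Under the orientation that the SAP points to, the rule is unusable as written (0.28% where 96.6% is correct) but gives the right size if the difference is squared or the missing minus sign is supplied, so the slip may have no numerical effect. Under the opposite orientation, every interim result with t1 from 0 to 23.8 goes to 480, including the 61% of trials under the planned effect in which 405 is enough. The cost there is up to 480 − 405 = 75 unnecessary patients, in that case only. These sizes assume the planned effect of 0.343, an interim near 202.5 patients and conditional power at the stage 1 estimate.

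Type 1 error is not affected: the weights are fixed and the final test is written correctly. The point should be fixed before the interim, but it does not threaten the validity of the primary test.

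**What to change.** First check the formula in the source PDF and any convention in SAP Section 8.3. Then, before the interim is run, state in Section 6 which sign of t1 and t2 favours CR845, and print the matching criterion:

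- positive favours CR845: t2 ≥ (1.96 − √0.5·t1)/√0.5; or
- negative favours CR845: −t2 ≥ (1.96 + √0.5·t1)/√0.5.

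Both agree exactly with Z_CHW. The second keeps the printed right-hand side and fits the direction implied by the programming plan. The cost is one sign and one sentence in the SAP, with no additional patients or data.

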7. ANALYSIS POPULATIONS

Several analysis populations are described below. The analysis of the Full Analysis and Per Protocol populations will be based on planned (randomized) treatment, the analysis of the Safety population will be based on actual treatment received.

7.1. ENROLLED POPULATION

The **enrolled population** consists of all individuals who signed the informed consent form.

7.2. EFFICACY POPULATIONS

7.2.1. Full Analysis Population (FAP)

The Full Analysis population (FAP) consists of all randomized patients who received at least 1 dose of double-blind study drug will be included in the efficacy evaluation.

7.2.2. Per Protocol (PP) Population

The Per Protocol population (PP) consists of all randomized patients in the FAP without any major protocol violations that could affect the efficacy analyses. The criteria for determining what constitutes a major protocol violation will be defined prior to database lock and the breaking of the blinded treatment assignment code.

The requirement for a PP population and exclusion of subjects from it will be decided at a blinded data review meeting (BDRM) and decisions will be documented in a separate BDRM document approved and signed by all authors of this SAP (or equivalents) prior to database lock and unblinding of the data.

